## **15.6 EXPLORATORY STUDIES**

FES-PET imaging correlative studies will be performed at baseline and after treatment to assess ER occupancy and establish correlations with anti-tumor activity and other tumor biopsy-based biomarkers of response.

*Archival and biopsy tissues will be analyzed to assess correlation of efficacy with molecular markers related to the mechanism of action of GDC-0810 and include alterations in DNA mutational status, RNA expression levels, DNA copy number, and protein expression.*

Matched biopsies pre- and on-treatment of safely accessible metastatic sites will be collected to assess for downstream indicators of ER target gene modulation, ER and PR protein levels, and Ki67 (tumor cell proliferation). These biomarkers will be measured at baseline and on-treatment to explore the association between changes in the tumor biomarkers as a PD readout of drug activity and objective response rate. Post-progression biopsies, whenever feasible and safely accessible, will be collected to assess for markers correlating to drug resistance.

Circulating tumor DNA will be analyzed for mutational status of, *but not limited to*, ER- $\alpha$  and PIK3CA to gain insights into potential causal relationships between GDC-0810's clinical activity and resistance mechanisms to endocrine therapy.

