### **11.1.8 Tumor Assessments**

Disease assessments will be performed at screening, *per institutional guidelines, and as clinically indicated*.

Imaging studies will include a CT scan of the chest, abdomen, and pelvis, plus a bone scan. At screening, a CT/MRI brain should be obtained if clinically indicated to rule out newly diagnosed, untreated brain metastasis.

Radiographic confirmation of objective tumor response or disease progression will be based on RECIST v1.1 ([Eisenhauer et al. 2009](#)).

The same method of assessment and the same technique should be used at screening and during follow up. Intravenous (IV) contrast is required when not medically contraindicated. Patients who have a contraindication to IV contrast may have MRI exams of the abdomen and pelvis performed in lieu of CTs and a non-contrast CT of the chest. Tumor evaluation by PET scan or by ultrasound may not substitute for CT or MRI scans. However, a CT for tumor assessment may be acquired on a PET/CT scanner if it is of full diagnostic quality and includes IV contrast.

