#### **11.5.2.2 Phase IIa**

All Cohort A patients with safely accessible soft tissue and/or visceral metastases will be required to have tumor biopsies. Optional tumor biopsies will be collected for Cohort B patients with safely accessible soft tissue and/or visceral metastases. Biopsies should be performed predose, at Cycle 3 (Day  $8 \pm 1$  day for patients in Cohort A1), and if feasible, at the time when disease progression is suspected (especially if disease progression occurs prior to Cycle 3). Biopsies should be collected during the period between  $\geq 2$  and  $\leq 12$  hours postdose.

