### **15.2.2 Phase IIa**

At the RP2D, a total of approximately 100 patients *have been* enrolled to further assess the safety, tolerability, preliminary evidence of anti-tumor activity, and exploratory PD markers of response of GDC-0810 in 3 distinct patient populations (Cohorts A1 and A2 will be combined for analysis purposes).

A total of 100 patients in Phase IIa will provide a more robust safety profile as well as sample size for preliminary assessment of anti-tumor activity based on clinical benefit rate (CBR) (see [Table 13](#)), defined as the percentage of patients achieving confirmed RECIST v1.1 defined complete response, partial response, and/or stable disease  $\geq 24$  weeks.

In Cohort A, because the presence of ESR1 mutations are associated with poor prognosis, an objective response rate (ORR), defined as the percentage of patients achieving confirmed complete and/or partial responses of at least 15% (5 out of 30 patients) would be considered of more clinical interest than CBR to warrant further development of GDC-0810 in this mutant patient population.

In Cohort B1, the desired observed CBR is 50%, based on historical CBRs of 46% ([Di Leo et al. 2010](#)) and 48% ([Bachelot et al. 2012](#)) for patients with ER+/HER2– advanced breast cancer after prior treatment with aromatase inhibitors.

In Cohort B2, the desired observed CBR is 20%, based on historical CBRs ranging from 18% to 26% for patients with ER+/HER2– advanced breast cancer after prior treatment with fulvestrant ([Baselga et al. 2011](#); [Yardley et al. 2013](#)).

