### **15.5 ANTI-TUMOR ACTIVITY**

Objective response and clinical benefit rates will be derived according to RECIST v1.1 and summarized by dose level and cohort. Progression-free survival will be listed for all patients in Phase IIa, when appropriate.

Objective response is defined as a complete response or partial response, as determined by investigator assessment and confirmed by repeat assessment  $\geq 4$  weeks after initial documentation. Patients with missing baseline or no response assessments will be classified as non-responders.

CBR is defined as the percentage of patients achieving confirmed RECIST v1.1-defined complete response, partial response, and/or stable disease  $\geq 24$  weeks.

Progression-free survival is defined as the time from the first day of study treatment with GDC-0810 in the Phase IIa until documented disease progression or death, whichever occurs first. For patients who do not have documented progressive disease or death before the end of the study or who are lost to follow-up, progression-free survival will be censored at the day of the last tumor assessment.

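### Section 15.6 relates change in matched-biopsy markers to yes/no objective response alone, which at the Cohort A level of interest keeps under half of the information in a continuous shrinkage measure

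*Combined protocol and SAP*

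**What the plan says.** The matched-biopsy sentence of Section 15.6 (Exploratory Studies) names one efficacy variable. Marker changes between the pre-treatment and on-treatment samples are used to "explore the association between changes in the tumor biomarkers as a PD readout of drug activity and objective response rate". Section 15.5 makes that variable binary: "Objective response is defined as a complete response or partial response, as determined by investigator assessment and confirmed by repeat assessment" at least 4 weeks later. Patients with no baseline or no response assessment count as non-responders. Section 15.5 also derives clinical benefit and progression-free survival, but no section defines percentage change in lesion size.

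Two other sentences of Section 15.6 are wider. One reads "Archival and biopsy tissues will be analyzed to assess correlation of efficacy with molecular markers related to the mechanism of action of GDC-0810", and its markers include "alterations in DNA mutational status, RNA expression levels, DNA copy number, and protein expression". The other uses FES-PET to "establish correlations with anti-tumor activity and other tumor biopsy-based biomarkers of response". Neither says which efficacy measure is meant, and neither mentions change from baseline in the biopsy markers.

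On who supplies pairs, Section 11.5.2.2 states: "All Cohort A patients with safely accessible soft tissue and/or visceral metastases will be required to have tumor biopsies". Biopsies are optional in Phase Ia and Cohort B and mandatory where accessible in Phase Ib (Sections 11.5.2.1 to 11.5.2.3). No number of pairs is given.

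For Cohort A, Section 15.2.2 sets "complete and/or partial responses of at least 15% (5 out of 30 patients" as the response rate that would justify further development. Table 13 shows it as an assumed observed 15% with an 80% interval of 8.34% to 28.74%. Section 15.1 plans no confirmatory inference and no imputation.

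**The concern.** Response under RECIST v1.1 is, for patients with target lesions, largely a cut of a continuous quantity: the change in the sum of their diameters. At the Cohort A level of interest the cut is very uneven. With 15 to 30 pairs it would leave about 15 × 0.15 = 2.25 to 30 × 5/30 = 5 responders to compare with everyone else. A patient whose tumors shrink markedly but fall short of a partial response is then treated the same as one who progresses.

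At stake is how much the paired samples can say about whether target modulation tracks tumor shrinkage. Some patients must undergo an invasive procedure to provide those samples. Enrollment has ended, so precision cannot be recovered by adding pairs; the choice of outcome is what remains open.

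**Working it through.** **Plan's own figure.** The exact (Clopper–Pearson) 80% limits for x responders in n are the Beta(x, n−x+1) quantile at 0.10 and the Beta(x+1, n−x) quantile at 0.90. With x = 5 and n = 30 this gives 8.34% and 28.74%, matching Table 13. The row labelled 15% is therefore 5/30 = 16.7%. Both rates are carried forward.

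**Inputs.** From the documents: response proportion p = 0.15 or 5/30, and the outcome named in Section 15.6. Assumed, because the documents do not give them: 15 to 30 evaluable pairs, bivariate-normal marker change and best tumor change with correlation ρ, responders being the best fraction p, and a two-sided 5% level used only as a yardstick.

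**Information kept.** Cutting a normal variable at proportion p multiplies its correlation with the marker by φ(z)/√[p(1−p)], where φ(z) is the normal density at the cut. The squared factor is the share of information kept.

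- p = 0.15: factor 0.653, squared 0.426.
- p = 5/30: factor 0.670, squared 0.449.
- At the ends of the Table 13 interval, 8.34% and 28.74%: 0.31 and 0.57.

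This share does not depend on the number of pairs or on ρ.

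**Power on the yardstick at ρ = 0.5.** Each cell gives continuous versus yes/no; ranges cover the two response rates. The rank tests are Spearman and exact Mann–Whitney. The parametric tests are Pearson and point-biserial. All values come from simulation.

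| Pairs | Rank tests | Parametric tests |
|---|---|---|
| 30 | 77% v 39–41% | 83% v 43–44% |
| 20 | 57% v about 25% | 64–65% v 28–30% |
| 15 | 43–44% v 15–17% | 50% v 21–22% |

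**Where the yes/no analysis does better.** With 30 pairs and p = 5/30, its power is 57% (rank) to 61% (parametric) at ρ = 0.6, and 77% (parametric) at ρ = 0.7. At ρ = 0.5 with p = 5/30, the rank test reaches about 59% with 45 pairs and about 74% with 60.

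**Pairs for 80% power at ρ = 0.5 (Fisher z).** n = [(1.960 + 0.842)/atanh(r)]² + 3. With r = 0.5 this gives 30 after rounding up. With r = 0.5 × 0.670 = 0.335 it gives 68.

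**Chance of 0 or 1 responder.** (1−p)ⁿ + np(1−p)ⁿ⁻¹ is 26–32% with 15 pairs, 13–18% with 20 and 3–5% with 30.

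**The case against.** Several objections stand and limit the point.

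- *A reader might infer that the plan forecasts about 5 responders in 30.* It does not. Section 15.2.2 gives the rate that would warrant further development, and Table 13 uses it to illustrate an interval. At a true rate of 15%, the chance of 5 or more in 30 is only 48%.
- *A reader might infer that the comparison is confined to Cohort A.* The sentence names no cohort. Pairs may also come from Phase Ia, Phase Ib and Cohort B, so the pool could exceed 30, and response rates outside Cohort A are not given.
- *A reader might infer that a real link is likely to be missed.* That depends on ρ and the number of pairs, neither of which is in the documents. It fails at 30 pairs with ρ of 0.6 or more.
- *No test is planned.* Section 15.1 is descriptive, so no stated power is breached. Imprecision still affects a descriptive estimate that rests on a handful of responders.
- *The biopsies have other uses.* Section 11.5.2 lists histology, ER degradation, PR, Ki67, target-gene modulation and sequencing. Showing that a marker moves on treatment needs no response outcome.
- *Clinical benefit is already derived.* A cut near 50%, the Cohort B1 figure, would keep about 64% under the same model (φ(0)²/0.25 = 0.637). Clinical benefit also depends on how long disease stays stable, so that figure is only a guide, and the matched-biopsy sentence does not name it.

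The wider efficacy sentence in Section 15.6 weakens the point without answering it, because it defines no measure and does not mention change. Section 11.1.8 requires that "The same method of assessment and the same technique should be used at screening and during follow up". That supports comparable measurements over time, but it does not show that lesion sums are held in the database.

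**Conclusion.** The point holds for the matched-biopsy sentence of Section 15.6, not for the whole section. Tying within-patient marker change to confirmed response alone keeps about 43–45% of the information at the Cohort A level of interest, and 31–57% across the Table 13 interval. At ρ = 0.5 with 15 to 30 pairs, illustrative power falls from roughly 43–83% to 15–44%.

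These figures rest on bivariate normality, an assumed correlation and an assumed number of pairs. They describe lost precision in an exploratory analysis. They do not show that the planned analysis would fail, or that any decision depends on it now that development has been halted. Low priority.

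**What to change.** In the matched-biopsy sentence of Section 15.6, replace objective response rate as the correlate with best percentage change from baseline in the sum of target-lesion diameters. Report it as a Spearman correlation with a confidence interval and a scatter plot by cohort for each marker. Keep objective response and clinical benefit as supportive groupings, and state that patients with pairs but no target lesion, or with no post-baseline measurement, appear only in those groupings.

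The cost is one amended sentence and one correlation and plot per marker, with no new scans, biopsies or patients. Before amending, confirm that target-lesion sums are available for analysis. The downside is that patients without a target lesion drop out of the correlation. Phase IIa admits patients with bone disease only, but pairs come from soft-tissue or visceral lesions, so these patients should be few. That last step is an assumption, and the report should give their number.

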## **16. DATA COLLECTION, RETENTION, AND MONITORING**

### **16.1 DATA COLLECTION INSTRUMENTS**

The Investigator will prepare and maintain adequate and accurate source documents designed to record all observations and other pertinent data for each patient treated with the study drug.

Study personnel at each site will enter data from source documents corresponding to a patient's visit into the protocol-specific electronic Case Report Form (eCRF) when the information corresponding to that visit is available. Patients will not be identified by name in the study database or on any study documents to be collected by the Sponsor (or designee) but will be identified by a site number, patient number, and initials.

If a correction is required for an eCRF, the time and date stamps *will* track the person entering or updating eCRF data and *will* create an electronic audit trail.

The Investigator is responsible for reviewing all information collected on patients enrolled in this study for completeness and accuracy. A copy of the eCRF will remain at the Investigator's site at the completion of the study.

## **16.2 DATA MANAGEMENT PROCEDURES**

The data will be entered into a validated database. The Sponsor-designated data management group will be responsible for data processing, in accordance with procedural documentation. Database lock will occur once quality assurance procedures have been completed.

All procedures for the handling and analysis of data will be conducted using good computing practices meeting FDA guidelines for the handling and analysis of data for clinical trials.

## **16.3 DATA QUALITY CONTROL AND REPORTING**

After data have been entered into the study database, a system of computerized data validation checks will be implemented and applied to the database on a regular basis. Queries are entered, tracked, and resolved through the EDC system directly. The study database will be updated in accordance with the resolved queries. All changes to the study database will be documented.

## **16.4 ARCHIVAL OF DATA**

The database is safeguarded against unauthorized access by established security procedures; appropriate backup copies of the database and related software files will be maintained. Databases are backed up by the database administrator in conjunction with any updates or changes to the database.

At critical junctures of the protocol (e.g., production of interim and final reports), data for analysis are locked and cleaned per established procedures.

An independent radiologic review facility will be used for the purpose of collecting and assessing the quality of patient scans throughout the trial. The review facility will retain copies of scans for centralized assessments of FES-PET and tumor assessment scans.

## **16.5 AVAILABILITY AND RETENTION OF INVESTIGATIONAL RECORDS**

To enable evaluations and/or audits from regulatory authorities or the Sponsor, the Investigator agrees to keep records, including the identity of all participating subjects (sufficient information to link records, e.g., CRFs and hospital records), all original signed informed consent forms, copies of all CRFs, safety reporting forms, source documents, and detailed records of treatment disposition, and adequate documentation of relevant correspondence (e.g., letters, meeting minutes, telephone calls, and reports). The records should be retained by the Investigator according to ICH, local regulations, or as specified in the Clinical Trial Agreement, whichever is longer, but at a minimum, all study

**GDC-0810—Genentech, Inc.**

123/Protocol GO29642, Version 9

documentation must be retained for 2 years after the last marketing application approval in an ICH region or after at least 2 years have elapsed since formal discontinuation of clinical development of GDC-0810.

If the Investigator becomes unable for any reason to continue to retain study records for the required period (e.g., retirement, relocation), the Sponsor should be prospectively notified. The study records must be transferred to a designee acceptable to the Sponsor, such as another investigator, another institution, or to the Sponsor itself. The Investigator must obtain the Sponsor's written permission before disposing of any records, even if retention requirements have been met.

## **16.6 MONITORING**

Monitoring visits will be conducted by representatives of the Sponsor according to the U.S. CFR Title 21 Parts 50, 56, and 312 and ICH Guidelines for GCP (E6). By signing this protocol, the Investigator grants permission to the Sponsor (or designee), and appropriate regulatory authorities to conduct on-site monitoring and/or auditing of all appropriate study documentation.

## **16.7 PATIENT CONFIDENTIALITY**

The Sponsor maintains confidentiality standards by coding each patient enrolled in the study through assignment of a unique patient identification number. This means that patient names are not included in data sets that are transmitted to any Sponsor location.

Patient medical information obtained by this study is confidential and may be disclosed to third parties only as permitted by the Informed Consent Form (or separate authorization for use and disclosure of personal health information) signed by the patient, unless permitted or required by law.

Medical information may be given to a patient's personal physician or other appropriate medical personnel responsible for the patient's welfare, for treatment purposes.

Data generated by this study must be available for inspection upon request by representatives of the U.S. FDA and other national and local health authorities, Sponsor monitors, representatives, and collaborators, and the IRB/EC for each study site, as appropriate.

## **17. ADMINISTRATIVE, ETHICAL, REGULATORY CONSIDERATIONS**

Clinical Practice and the principles of the Declaration of Helsinki, or the laws and regulations of the country in which the research is conducted, whichever affords the greater protection to the individual. The study will comply with the requirements of the ICH E2A guideline (Clinical Safety Data Management: Definitions and Standards for Expedited Reporting). Studies conducted in the United States or under a U.S.

Investigational New Drug (IND) application will comply with U.S. FDA regulations and applicable local, state, and federal laws. Studies conducted in the European Union (E.U.) or European Economic Area will comply with the E.U. Clinical Trial Directive (2001/20/EC).

## **17.1            PROTOCOL AMENDMENTS**

Any protocol amendments will be prepared by the Sponsor. Protocol amendments will be submitted to the IRB/EC and to regulatory authorities in accordance with local regulatory requirements.

Approval must be obtained from the IRB/EC and regulatory authorities (as locally required) before implementation of any changes, except for changes necessary to eliminate an immediate hazard to patients or changes that involve logistical or administrative aspects only (e.g., change in Medical Monitor or contact information).

## **17.2            PROTOCOL DEVIATIONS**

*The investigator should document and explain any protocol deviations. The investigator should promptly report any deviations that might have an impact on patient safety and data integrity to the Sponsor and to the IRB/EC in accordance with established IRB/EC policies and procedures. The Sponsor will review all protocol deviations and assess whether any represent a serious breach of Good Clinical Practice guidelines and require reporting to health authorities. As per the Sponsor's standard operating procedures, prospective requests to deviate from the protocol, including requests to waive protocol eligibility criteria, are not allowed.*

## **17.3            INSTITUTIONAL REVIEW BOARDS OR ETHICS COMMITTEE**

The protocol, Investigator's Brochure, the consent forms, any information to be given to the patient (including patient recruitment materials), and relevant supporting information must be submitted to the IRB/EC by the Investigator for review and approval before the study is initiated. The IRB's/EC's unconditional approval statement will be transmitted by the Investigator to the Sponsor or designee prior to the shipment of study supplies to the site. This approval must refer to the study by exact protocol title and number and should identify the documents reviewed and the date of review.

Protocol and/or informed consent modifications or changes may not be initiated without prior written IRB approval except when necessary to eliminate immediate hazards to the patients or when the change(s) involves only logistical or administrative aspects of the study. Such modifications will be submitted to the IRB, and written verification that the modification was submitted and subsequently approved should be obtained.

Investigators are required to promptly report to their respective IRB/EC all unanticipated problems involving risk to human patients. Some IRBs/ECs may want prompt notification of all serious adverse events, whereas others require notification only about

events that are serious, assessed to be related to study treatment, and are unexpected. Investigators may receive written IND safety reports or other safety-related communications from the Sponsor. Investigators are responsible for ensuring that such reports are reviewed and processed in accordance with regulatory requirements and with the policies and procedures established by their IRB and archived in the site's Study File.

Finally, the Investigator will keep the IRB/EC informed as to the progress of the study, revisions to documents originally submitted for review, annual updates, and/or request for re-approvals, and when the study has been completed.

